- Viral load one day and one week after the last session
- Chest Xray changes one day and one week after the last session
- Percentage of patients with positive IgG serology one day and one week after the last session
- Percentage of patients with positive IgM serology one day and one week after the last session
- Pulmonary function test one day and one week after the last session
- Time to symptoms recovery
- Percentage of patients who required invasive intubation
- Time to recovery (negative PCR twice) – TTCR
- Mortality rate in 30 days
- Safety – percentage of adverse events

STUDY DESIGN

Subjects: Patients at Maimonides Medical Center (MMC)

Eligibility Criteria:

Patients who are (1) within 7 days of need of oxygen supply, (2) positive to SARS-CoV-2 through RT-PCR, (3) have at least one risk factor for bad prognosis of COVID-19: hypertension, diabetes mellitus, ischemic heart disease, smoking, age>50, etc., (4) have respiratory insufficiency: Room Air SpO₂ <94% or PaO₂/FiO₂<300mmHg, (5) are older than 18 years of age and (6) have ability to sign an informed consent will be included in the study.

Patients who are (1) negative to SARS-CoV-2 through RT-PCR, (2) have a HBOT contraindication: pneumothorax, pneumomediastinum, claustrophobia, ear/sinus disease which aren't allowed in HBOT, known chronic pulmonary disease: severe emphysema or known pulmonary bullae, (3) have pregnancy and/or (4) have inability to sign an informed consent will be excluded from study.

Design:

This study is a prospective randomized controlled, double blind clinical trial performed on laboratory confirmed COVID-19 infection admitted patients in MMC. It involves the use of MMC monoplace HBO chambers. The trial will include 30 patients who will undergo either hyperbaric oxygen therapy (HBOT) or Normobaric oxygen therapy (NBOT), randomized on a 2:1 ratio, within 4 days in addition to the standard treatment including oxygen, drugs, steroids, bronchodilators, antibiotics and others.

The evaluation procedure includes symptom monitoring, room air saturation, vital signs monitoring, pulmonary function and blood tests at baseline, one day and one week after the last session. In addition, one hour prior to and post session saturation and vitals will be monitored.

Data Collection Procedures:

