Upon signing an informed consent, the patients will be randomized 2:1 to hyperbaric oxygen therapy group (HBOT) and normobaric oxygen therapy group (NBOT) (Randomization will be performed using a computer software based on patient id). Following the randomization, the patients will undergo evaluation including symptoms, vitals, pulmonary function, blood tests.

The patients will undergo 8 sessions of either hyperbaric/normobaric oxygen therapy, 2 sessions per day, in 4 consecutive days. During the sessions, the symptoms and vitals will be monitored. 1 day and 1 week following the last session, reevaluation will be performed.

Protocol Day 1

1. Baseline evaluation: blood test including: arterial blood gases, 2 CBC tubes, 2 Gel tubes (10-15 cc total), vitals (temperature, blood pressure, heart rate, room air saturation), symptoms questionnaire, pulmonary function test.
2. Vitals (temperature, blood pressure, heartrate, room air saturation) one hour prior to session
3. One-hour session NBO/HBO
4. Vitals (temperature, blood pressure, heartrate, room air saturation) one hour after the session.
5. Vitals (temperature, blood pressure, heartrate, room air saturation) one hour before the 2nd session.
6. One-hour session NBO/HBO (8 hours following the first session)
7. Vitals (temperature, blood pressure, heartrate, room air saturation) one hour after the session.
8. Daily oxygen supply dose monitoring.

Protocol Day 2-4

1. Daily symptoms questionnaire
2. Vitals (temperature, blood pressure, heartrate, room air saturation) one hour prior to session
One-hour session NBO/HBO
3. Vitals (temperature, blood pressure, heartrate, room air saturation) one hour after the session.
4. Vitals (temperature, blood pressure, heartrate, room air saturation) one hour before the 2nd session.
5. One-hour session NBO/HBO (8 hours following the first session)
6. Vitals (temperature, blood pressure, heartrate, room air saturation) one hour after the session.
7. Daily oxygen supply dose monitoring.

Follow up Protocol

1. Repeat evaluations one day after the last session and one week after the last session:
 - Blood test including: arterial blood gases, 2 CBC tubes, 2 Gel tubes (10-15 cc total)
 - Vitals (temperature, blood pressure, heart rate, room air saturation)
 - Symptoms questionnaire
 - Pulmonary function test.
2. Oropharyngeal swab for SARS-CoV-2 RT-PCR every 3 days for 1 week
3. Clinical monitoring for 30 days

Data Analysis:

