Continuous data will be expressed as means \pm standard-deviations. Independent and dependent t-test with two-tail distribution will be performed to compare variables between and within the two groups, when a normality assumption holds according to Kolmogorov-Smirnov test. Categorical data will be expressed in numbers and percentages and compared by chi-square tests. Univariate analyses were performed using Chi-Square/Fisher's exact test to identify significant variables. A value of $p<0.05$ will be considered significant.

Data analysis will be performed with Matlab R2019b (Mathworks, Natick, MA) Statistics Toolbox.

Sample Size: 30

Based on a previous study on HBOT effect on ARDS [14], with 95% power and significance level of 5%, and a groups difference of 30 (SD 15-18) in the PaO₂/FiO₂ and a 2:1 groups allocation, the sample requires 7 NBOT patients and 13 HBOT patients. Considering 15% dropout, we will recruit 10 NBOT patients and 20 HBOT patients, 30 in total.

Expected Outcomes:

The primary outcomes measures that will be accessed in the study are:

- Oxygenation index = PaO₂/FiO₂ one day after the last session.
- SpO₂ – room air saturation one hour before and after a session, 6 hours after a session and one day after the last session.
- NES – Early warning score, before and after each session, 6 hours after each session and one day after the last session
- Inflammatory parameters one day after the last session: WBC, Immune profile, CRP, ESR, Procalcitonin, TNF α , IL1, IL2, IL6, IL10.

The secondary outcomes measures that will be accessed in the study are:

- Oxygenation index = PaO₂/FiO₂ one week after the last session.
- SpO₂ – room air saturation one week after the last session.
- NES – Early warning score, one week after the last session
- Inflammatory parameters one week after the last session: WBC, Immune profile, CRP, ESR, Procalcitonin, TNF α , IL1, IL2, IL6, IL10.
- Symptoms level one day and one week after the last session
- Viral load one day and one week after the last session
- Chest Xray changes one day and one week after the last session
- Percentage of patients with positive IgG serology one day and one week after the last session
- Percentage of patients with positive IgM serology one day and one week after the last session
- Pulmonary function test one day and one week after the last session
- Time to symptoms recovery
- Percentage of patients who required invasive intubation
- Time to recovery (negative PCR twice) – TT_{CR}

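### Prespecify a baseline-adjusted between-arm analysis as the deciding test, and label the paired within-arm t-tests as descriptive

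*Combined protocol and SAP*

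**What the plan says.** The Data Analysis section of the combined protocol and SAP gives one rule for continuous outcomes: "Independent and dependent t-test with two-tail distribution will be performed to compare variables between and within the two groups, when a normality assumption holds". Significance is p<0.05 throughout. No covariate or change-score analysis is mentioned. The section does not say which of the two kinds of test supports an efficacy conclusion, and it does not call the paired tests descriptive.

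Baseline values are scheduled. The Design section lists "pulmonary function and blood tests at baseline, one day and one week after the last session". Protocol Day 1 opens with "Baseline evaluation: blood test including: arterial blood gases, 2 CBC tubes, 2 Gel tubes", and then has "Vitals (temperature, blood pressure, heartrate, room air saturation) one hour prior to session". This evaluation comes after randomization but before any treatment session. Blood gases are listed; the FiO2 at the time of the draw is not.

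The outcomes in Expected Outcomes are worded as post-treatment values, for example "Inflammatory parameters one day after the last session: WBC, Immune profile, CRP, ESR, Procalcitonin". Some are measured around every session, such as the "Early warning score, before and after each session, 6 hours after each session and one day after the last session".

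Both arms receive oxygen sessions "in addition to the standard treatment including oxygen, drugs, steroids, bronchodilators, antibiotics and others". The Sample Size paragraph assumes a "groups difference of 30 (SD 15-18") in PaO2/FiO2, 2:1 allocation, 13 HBOT and 7 NBOT evaluable patients, and 20 and 10 recruited.

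**The concern.** Two matters of unequal weight sit in one sentence.

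First, the between-arm comparison leaves out a baseline that the trial already collects. With 30 patients, chance differences between the arms at baseline and ordinary between-patient spread both widen the interval. A prespecified adjustment could recover some of that precision at almost no cost.

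Second, a paired test within one arm asks whether that arm changed over time. It does not ask whether hyperbaric differs from normobaric oxygen. Patients in both arms are treated actively, so a shared change over the four treatment days is plausible. For the same true change, the arm with 20 patients reaches p<0.05 more easily than the arm with 10. A report that HBOT improved significantly and NBOT did not could then follow from the allocation ratio alone, and the plan as written leaves room for it.

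**Working it through.** **Inputs from the protocol.** Difference 30 and SD 15 to 18 for PaO2/FiO2; two-sided 5%; 20 vs 10 recruited; 13 vs 7 evaluable; 15% dropout, which leaves about 17 vs 8.

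**Assumed, because the documents do not give them.** The baseline-to-follow-up correlation r; the size of any change common to both arms, in SDs of change; equal SDs in both arms and at both times; SD 18 read as the SD of the post-treatment value (the alternative is shown in step 2).

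**1. The plan's own figure.** Noncentral-t power for a difference of 30, unadjusted:

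| HBOT vs NBOT | SD 15 | SD 18 |
|---|---|---|
| 13 vs 7 | 98.1% | 91.9% |
| 17 vs 8 | 99.4% | 96.1% |
| 20 vs 10 | 99.9% | 98.6% |

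At 13 vs 7 and a mid-range SD of 16.5, power is 95.6%. The stated 95% is therefore reproduced for SDs in the middle of the stated range.

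**2. What adjustment buys.** The unadjusted half-width is t(0.975, 28) × SD × √(1/20 + 1/10) = 2.048 × 18 × 0.387 = 14.28 if the sample SD equals 18 exactly. Averaged over simulated trials it is 14.15, because the sample SD averages slightly below the true SD. ANCOVA has residual SD = 18 × √(1 − r²) on 27 degrees of freedom, plus a small term for chance baseline imbalance. Mean half-widths in mmHg (100,000 simulated trials per cell):

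| | Unadjusted | r=0 | r=0.2 | r=0.3 | r=0.5 | r=0.7 |
|---|---|---|---|---|---|---|
| 20 vs 10 | 14.15 | 14.43 | 14.15 | 13.76 | 12.50 | 10.31 |
| 17 vs 8 | 15.79 | 16.19 | 15.85 | 15.45 | 14.02 | 11.56 |

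At 20 vs 10 the worst case is 14.43/14.15 = 1.02, a 2% loss. The gain is 1 − 12.50/14.15 = 12% at r=0.5 and 1 − 10.31/14.15 = 27% at r=0.7. Break-even is near r=0.2. At 13 vs 7 and SD 18, power moves from 91.9% unadjusted to 90.1%, 92.6%, 96.3% and 99.5% at r = 0, 0.3, 0.5 and 0.7.

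If 18 is instead the SD of change, the post-value SD is 18/√(2(1 − r)) = 15.2, 18.0 and 23.2 at r = 0.3, 0.5 and 0.7. Half-widths at 20 vs 10 then go from 11.97 to 11.65, from 14.15 to 12.50, and from 18.27 to 13.31.

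**3. Validity of the between-arm test.** With no treatment difference, simulation at 13 vs 7 and SD 18 gave about 5% false positives for both the t-test and ANCOVA (0.050 to 0.053). No bias is being corrected.

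**4. What the paired tests can show when the arms do not differ.** Let p20 and p10 be the noncentral-t probabilities that a paired test is significant with 20 and with 10 patients. The arms are independent, so P(HBOT only) = p20 × (1 − p10) and P(NBOT only) = p10 × (1 − p20).

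| Common change (SD) | p20 | p10 | HBOT only | NBOT only |
|---|---|---|---|---|
| 0 | 0.050 | 0.050 | 4.75% | 4.75% |
| 0.2 | 0.136 | 0.088 | 12% | 8% |
| 0.4 | 0.397 | 0.205 | 32% | 12% |
| 0.6 | 0.721 | 0.396 | 44% | 11% |
| 0.8 | 0.924 | 0.616 | 35% | 5% |
| 1.0 | 0.989 | 0.803 | 19% | 1% |

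For example, at 0.4 SD: 0.397 × 0.795 = 0.316 and 0.205 × 0.603 = 0.124. At 17 vs 8 the pairs are 28% vs 11% (0.4 SD) and 44% vs 11% (0.6 SD). With 15 vs 15 they would be equal: 21% each and 24% each.

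**5. Does the randomized comparison agree?** Among simulated 20 vs 10 trials that show significance in HBOT only, with no true difference, the between-arm t-test of change is significant in 23% at a common change of 0, 13% at 0.2, 7.0% at 0.4, 5.6% at 0.6 and 10% at 1.0 SD.

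**The case against.** - **The plan is not silent on the contrast.** The sample size is built on a between-group PaO2/FiO2 difference in a randomized controlled trial. This stands, and it points to the between-arm test. It is indirect, though, and covers one outcome, while SpO2, the early warning score and the inflammatory markers are also listed as primary.
- **Adjustment is a preference.** The t-test is valid, power is already high, no r is given, and ANCOVA gains nothing below r of about 0.2. All of this stands, and on its own this part would be minor. It is worth making because the data are already collected and the worst-case loss is about 2%.
- **The misleading report is hypothetical.** A reader might infer that the protocol intends to claim efficacy from the paired tests. It does not say so. It only fails to rule this out. The 32% and 44% figures also depend on an assumed common change: at 1.0 SD the figure is 19%, and at 1.67 SD it is 0.3%.
- **A real effect would reconcile the tests.** With the protocol's full difference, read as 30/18 = 1.67 SD of change, and a common change of 0.4 SD, significance in HBOT only is accompanied by a significant between-arm test in 99.7% of simulated trials. This is correct. The concern is with a small or absent effect.
- **Paired tests have another use.** Saturation and the early warning score are measured around each session, and those are natural within-patient contrasts. This stands: the paired tests may remain as description, provided the same outcomes are also compared between arms.

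**Conclusion.** The point holds as a recommended clarification. The Data Analysis section omits a baseline that is already collected, tests within-arm change at the same threshold as the between-arm difference, and does not say which test decides.

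The precision gain ranges from a 2% loss at r=0 to a 27% narrower interval at r=0.7, under an assumed r. The interpretive risk is larger: at common changes of 0.2 to 1.0 SD, significance in HBOT only has probability 12% to 44% with no treatment difference, against 1% to 12% for NBOT only. In that range the between-arm test is significant in only about 6% to 13% of the HBOT-only trials. With no common change the two patterns are equally likely. These figures rest on an assumed equal true change and equal SDs.

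Three stronger readings are not supported. The unadjusted t-test is not biased. The trial does not need adjustment to have adequate power at 20 vs 10. The protocol does not declare the paired tests to be efficacy evidence. The Kolmogorov-Smirnov condition, values below assay limits and missing baselines are separate matters and are not part of this point.

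**What to change.** Add two statements to the Data Analysis section.

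(a) *PaO2/FiO2 on the day after the final session is analysed by ANCOVA with terms for arm and the Day 1 pre-session PaO2/FiO2. The adjusted difference, its 95% CI and p-value are reported. The same model is used for SpO2 and for each quantitative inflammatory marker that has a Day 1 value.* State that the covariate is the value taken after randomization and before the first session, and add FiO2 at the blood draw to the Day 1 schedule. A Day 1 early warning score is not named in the schedule, so adjustment for it depends on one being recorded.

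(b) *Efficacy conclusions rest on between-arm comparisons only. Paired within-arm tests, including contrasts around individual sessions, are descriptive. Outcomes measured around sessions are also compared between arms.*

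No outcome, time point or patient is added or removed. The analysis cost is one degree of freedom (28 to 27) and an interval about 2% wider if r is near zero. The operational cost is recording FiO2 with the Day 1 gas.

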becomes significant and enables tissue oxygenation without the need of red blood cells]15[.

- **Mitochondrial function restoration** – HBOT can restore the normal function of the mitochondria and the cellular metabolism, decrease apoptosis and reduce the oxidative injury [16].
- **Anti-inflammatory** – HBOT reduces the following inflammatory cytokines both in the protein level and genes expression (mRNA): IL-2, TNF-alpha, IL-6, IL-1beta, mediated by several transcription factors: Hypoxia induced factor 1alpha (HIF1alpha), Nrf2, NFkB [17-19]. The anti-inflammatory effect has been shown in chronic diseases as well as models of acute infection and massive hemorrhage [20, 21].

Apart from Chen et al. case series, no prospective study was performed on the effect of HBOT on COVID-19 patients. In addition to the safety report in that case series, there's more evidence for the level of safety of HBOT in patients with acute pulmonary insufficiency:

- There is an ongoing debate in regards to the use of high inhaled oxygen level for patients with ARDS. In a recent randomized controlled trial (LUNGSafe), there was no association between high oxygen levels and bad prognosis]22[.
- The use of HBOT in patients with ARDS after blunt chest trauma, showed promising results in oxygenation and cardiac function, with no safety issues]14[.

STUDY OBJECTIVES

The purpose of the current study is to evaluate the efficacy of HBOT in moderate-severe non ventilated COVID-19 patients.

The primary objectives of study will be to assess the following indicators:

- Oxygenation index = $\text{PaO}_2/\text{FiO}_2$ one day after the last session.
- SpO_2 – room air saturation one hour before and after a session, 6 hours after a session and one day after the last session.
- NES – Early warning score, before and after each session, 6 hours after each session and one day after the last session
- Inflammatory parameters one day after the last session: WBC, Immune profile, CRP, ESR, Procalcitonin, TNFalpha, IL1, IL2, IL6, IL10.

The secondary objectives of study will be to assess the following indicators:

- Oxygenation index = PaO₂/FiO₂ one week after the last session.
- SpO₂ – room air saturation one week after the last session.
- NES – Early warning score, one week after the last session
- Inflammatory parameters one week after the last session: WBC, Immune profile, CRP, ESR, Procalcitonin, TNF_{alpha}, IL1, IL2, IL6, IL10.
- Symptoms level one day and one week after the last session

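### Four unranked primary outcome families (at least 13 variables) share one unadjusted 5% threshold, with no lead endpoint and no rule for what makes the trial positive

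*Combined protocol and SAP*

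**What the plan says.** Study Objectives gives the aim as a test of efficacy: "The purpose of the current study is to evaluate the efficacy of HBOT in moderate-severe non ventilated COVID-19 patients". It then introduces four bullets with "The primary objectives of study will be to assess the following indicators". Expected Outcomes repeats the same four under "The primary outcomes measures that will be accessed in the study are". Neither list is ranked.

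- **PaO2/FiO2** has a single time point, the day following the final session.
- **SpO2** is the second bullet, and its readings are set out as "room air saturation one hour before and after a session, 6 hours after a session and one day after the last session", so several time points are primary.
- **NES** is the third bullet, with its timing given as "before and after each session, 6 hours after each session and one day after the last session", again several time points.
- **The inflammatory panel** is the fourth bullet and opens with "Inflammatory parameters one day after the last session: WBC, Immune profile, CRP, ESR, Procalcitonin"; its five remaining items are TNF-alpha and the interleukins IL1, IL2, IL6 and IL10.

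Data Analysis sets one threshold for everything: "A value of $p<0.05$ will be considered significant". The tests are described as follows: "Independent and dependent t-test with two-tail distribution will be performed to compare variables between and within the two groups". Sample Size is worked out for PaO2/FiO2 alone.

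**The concern.** The document does not say which primary result, or which combination of them, would make the trial positive. It neither states nor excludes that one significant primary is enough. If PaO2/FiO2 fails, a favourable SpO2 reading, NES value or single cytokine could still be reported as a positive primary result at p<0.05.

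Two features widen the choice:

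- SpO2 and NES are each primary at several time points around the sessions, and Data Collection Procedures schedules eight sessions. SpO2 is worded for a session in the singular and NES for every session. No rule says which reading counts or how the readings are combined.
- The within-group t-tests use the same threshold. They do not compare HBOT with NBOT, and nothing limits what they may be used to support.

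**Working it through.** **Count of primaries.** There are four families. By variable the count is 1 (PaO2/FiO2) + 1 (SpO2) + 1 (NES) + 10 (panel) = 13. This is a minimum, because the immune profile is counted as one item and each repeated measure as one variable.

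**The plan's own sample size.** The inputs from Sample Size are a difference of 30, SD 15-18, 95% power, a 5% level and 2:1 allocation. The normal approximation for the NBOT arm is n = (1 + 1/2) × SD² × (1.960 + 1.645)² / 30².

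- SD 15: 1.5 × 225 × 12.99 / 900 = 4.87, so 5 NBOT and 10 HBOT.
- SD 18: 1.5 × 324 × 12.99 / 900 = 7.02, so 8 NBOT and 16 HBOT.

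With the noncentral t, the stated 7 NBOT and 13 HBOT give 98.1% power at SD 15, 95.6% at SD 16.5 and 91.9% at SD 18. The stated figure therefore reproduces near the middle of the SD range. It is a calculation for one endpoint tested once at 5%.

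**Error if any one primary may be claimed.** These are between-group tests only, two-sided 0.05 each, with no true effect on any outcome.

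- Independent tests: 1 − 0.95^k. For k = 4 this is 18.5%; for k = 13 it is 48.7%.
- Equal correlation ρ: 1 − E[(Φ((1.96 − √ρ X)/√(1−ρ)) − Φ((−1.96 − √ρ X)/√(1−ρ)))^k], with X standard normal, integrated numerically.

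| Assumed ρ | 0 | 0.5 | 0.7 | 0.9 |
|---|---|---|---|---|
| 4 tests (one per family) | 18.5% | 15.6% | 13.0% | 9.4% |
| 13 tests (one per variable) | 48.7% | 33.4% | 24.1% | 13.8% |

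A simulation of two-sample t-tests with 8 and 17 patients (40,000 runs) agrees: 18.5/16.1/13.4/9.8% for four tests and 49.0/34.4/24.7/14.1% for 13.

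**At 0.0125 per test** (0.05/4), for the same correlations: four tests give 4.9/4.3/3.7/2.6%, and 13 tests give 15.1/10.7/7.7/4.1%.

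**Power for PaO2/FiO2.** This uses the noncentral t with difference 30. Evaluable numbers after 15% dropout are 10 × 0.85 = 8.5, rounded down to 8 NBOT, and 20 × 0.85 = 17 HBOT.

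| NBOT/HBOT | Alpha | SD 15 | SD 18 |
|---|---|---|---|
| 8/17 | 0.05 | 99.4% | 96.1% |
| 7/13 | 0.05 | 98.1% | 91.9% |
| 8/17 | 0.0125 | 96.7% | 86.9% |
| 7/13 | 0.0125 | 91.7% | 77.2% |

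**The case against.** The strongest reply is that PaO2/FiO2 is already the lead in practice. It comes first in both lists and is the only outcome with an effect size, power and alpha. On that reading its comparison has 5% error, and the higher rates describe a decision rule that the plan never states. It is true that the rates are conditional. But sizing a trial on one variable does not confine the primary claim to it, and three other families carry the same label and threshold. If PaO2/FiO2 was meant as the lead, one sentence would say so.

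Four further points have some force.

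- **Correlations.** Full independence and a uniform 0.9 are both hard to credit across oxygenation, a clinical score and cytokines, so the middle columns are the better guide. The error is above 5% in every column.
- **Number of tests.** The plan uses t-tests only where normality holds and names no alternative for continuous data, so 13 counts variables rather than planned tests. The calculation needs only that each test has a 5% error rate. Repeated readings and within-group tests are left out, so the figures are not an upper bound.
- **Power.** The figures depend on the protocol's SD, which comes from a cited study of blunt chest injury that was not available. As illustrative assumptions, with 8/17 evaluable at 5%, an SD of 25 gives 76%, 30 gives 61% and 40 gives 39%.
- **Missing protocol.** Adverse Event Reporting ends by pointing to an overall-study protocol that was not supplied and might contain a hierarchy. The present document has its own analysis section and gives none.

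**Conclusion.** The concern holds for this document and should be fixed. As written, the plan allows any one of at least 13 primary variables to carry the efficacy claim, with no control of the overall error. If that is how success is judged, the nominal 5% becomes 9-19% with one test per family and 14-49% with one per variable. The range reflects assumed equal correlations from 0.9 to 0. The between-group comparison of PaO2/FiO2 remains valid at 5% if it alone decides the trial. What is missing is the statement that it does.

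**What to change.** Replace the general significance sentence in Data Analysis, and align Study Objectives and Expected Outcomes, with text such as:

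> The primary outcome is PaO2/FiO2 one day after the last session, compared between HBOT and NBOT at two-sided 5%. The trial is positive only if this comparison is significant. All other outcomes are secondary and are reported as between-group estimates with 95% confidence intervals, without a confirmatory claim. Within-group t-tests are descriptive and cannot support an efficacy claim.

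Move SpO2, NES and the inflammatory panel to secondary. Report SpO2 and NES at one day after the last session, which is already listed for both, and treat the per-session readings as descriptive.

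If the sponsor wants to keep four primaries, name one variable and one time point per family and choose one of these:

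- **Split alpha:** 0.0125 each, for a total of at most 5%. The limit of one variable per family is essential, because 13 tests at 0.0125 could still reach 15%.
- **Fixed sequence:** test in a pre-specified order starting with PaO2/FiO2, each at 5%, and stop at the first non-significant result. This also holds the overall error at 5% and leaves PaO2/FiO2 power unchanged.

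The cost is wording only, with no added patients or data. With a single primary, the other three families can no longer carry the primary claim. Splitting alpha lowers PaO2/FiO2 power at SD 18 from 96% to 87% (8/17 evaluable) or from 92% to 77% (7/13). These figures hold only if the protocol's difference and SD are right.

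### SpO2 and NES are primary at up to 25 readings each with no deciding time point or reference value, so a short-lived post-session rise could be reported as primary success

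*Combined protocol and SAP*

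**What the plan says.** Study Objectives and Expected Outcomes both list SpO2 as primary: "room air saturation one hour before and after a session, 6 hours after a session and one day after the last session". NES is primary "before and after each session, 6 hours after each session and one day after the last session". The other two primary items, PaO2/FiO2 and the inflammatory parameters, are read only one day after the last session. SpO2 and NES at one week are secondary.

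Data Collection Procedures sets out "8 sessions of either hyperbaric/normobaric oxygen therapy, 2 sessions per day, in 4 consecutive days". Protocol Day 1, item 6, times the second daily session: "One-hour session NBO/HBO (8 hours following the first session". Vitals, including room-air saturation, are taken one hour before and one hour after each session; item 5 is the reading "one hour before the 2nd session".

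Day 1 has two saturations taken before any study treatment. Item 1, the baseline evaluation, includes "vitals (temperature, blood pressure, heart rate, room air saturation), symptoms questionnaire, pulmonary function test". Item 2 is a further set of vitals one hour before the first session.

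Data Analysis states: "Independent and dependent t-test with two-tail distribution will be performed to compare variables between and within the two groups", provided a normality check is met, with significance at p<0.05. Neither it nor the outcome lists say which reading decides efficacy on SpO2 or NES, which value is the reference, or how the eight sessions are combined.

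**The concern.** The trial's stated purpose is efficacy. Listing before-session and after-session readings as primary, beside a planned paired test, invites a contrast between each session's own before and after values. For sessions 2 to 8 that reference value has itself been taken after study treatment. The contrast then answers whether saturation or score moves over one session, not whether the patient is better for having had the course.

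Because the day-after and per-session readings have the same rank, a rise present one hour after a session and gone by the next day would meet the plan's wording for a significant primary result. The paired test allows this even within one arm, without any randomised comparison. With the deciding reading left open, the choice could also be made after the data are seen.

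**Working it through.** **1. The plan's own figure.** Sample Size covers PaO2/FiO2 only: difference 30, SD 15-18, 95% power, two-sided 5%, allocation 2:1. With SD 18 in NBOT and 15 in HBOT, n(NBOT) = (1.960 + 1.645)² × (18² + 15²/2) / 30² = 12.995 × 436.5 / 900 = 6.30, so 7 NBOT, and 2 × 6.30 = 12.6, so 13 HBOT. The stated 7 and 13 are reproduced. No effect, SD or power is given for SpO2 or NES, so this figure is unaffected by the point.

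**2. Number of primary readings.** 8 sessions × 3 readings (before, after, 6 hours after) + 1 day-after reading = 25 per outcome, or 50 for the two. This is an upper count: the SpO2 wording refers to a session, the NES wording to each session.

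**3. How many before-session readings are untreated.** Only the one before session 1; 8 − 1 = 7 follow earlier study sessions. Taking one-hour sessions and a 24-hour cycle, with session 1 running from hour 0 to hour 1:

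| Reading of the 8-hour interval | Session 2 starts | Reading one hour before it | Time since session 1 ended | Next-morning before-reading, time since session 2 ended |
|---|---|---|---|---|
| Start to start | hour 8 | hour 7 | 6 h | 23 − 9 = 14 h |
| End to start | hour 9 | hour 8 | 7 h | 23 − 10 = 13 h |

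Under the start-to-start reading, the value 6 hours after the first daily session and the value one hour before the second are the same measurement. One number would be both an outcome and a reference on each of 4 days, leaving 25 − 4 = 21 distinct SpO2 times.

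**4. What a same-session contrast can show.** Let each session add g, and let a fraction r of the gain be kept at the next before-reading: post_k = pre_k + g and pre_(k+1) = r × post_k, with pre_1 = 0. The contrast post_k − pre_k equals g whatever r is. With g = 0.5 SpO2 point (assumed):

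| r | Each same-session change | Gain before session 8 | Gain after session 8 | Gain one day after |
|---|---|---|---|---|
| 1 | 0.5 | 7g = 3.5 | 8g = 4.0 | 4.0 |
| 0.5 | 0.5 | 0.992g = 0.50 | 1.992g = 1.00 | at most 0.50 |
| 0 | 0.5 | 0 | 0.5 | 0 |

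The contrast is identical in all three rows, while the day-after gain runs from 0 to 4.0.

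**5. A fading effect with explicit timing.** Assume each session adds 4 points that then decay exponentially, with start-to-start sessions. For half-lives of 1, 3 and 6 hours, the mean same-session change is 1.97, 2.89 and 3.09 points. The gain one day after the last session is 0.00, 0.02 and 0.37. The 4 points and the half-lives are assumptions; the documents give neither.

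**6. Schedule against outcome list.** Room-air saturation is scheduled at baseline and one day after the last session. No separate 6-hour reading is scheduled. At best, the reading before the second daily session supplies 4 of the 8, and nothing supplies it after the second daily session. NES is neither scheduled nor defined.

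**The case against.** The strongest reply is that the outcome lists say when SpO2 and NES are measured, not how they are analysed. No section defines a per-session change score, and the within-group test fits just as well with baseline against one day and one week. This stands: the same-session contrast is permitted, not mandated.

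A reader might infer that carry-over hides a lasting benefit from the trial, or that the design reverses the evidence by favouring fading effects over durable ones. The documents do not support either:

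- The day-after reading is part of the same primary outcome, so a lasting gain remains visible there.
- NBOT patients follow the same schedule, so a between-arm comparison at any fixed time is not biased by carry-over.
- The recursion in step 4 gives the same change for every r. The contrast is uninformative about durability, not reversed. The larger changes in step 5 reflect the larger assumed gain per session.
- Before-session readings are useful trough values: under full retention they climb to 3.5 points.

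It is also fair that same-session change is a legitimate description of acute response. What the reply does not meet is that acute and day-after readings carry equal primary rank, with nothing to say which one decides.

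**Conclusion.** The point holds as a defect in how the primary SpO2 and NES outcomes are defined. Up to 25 nominal readings per outcome can be tested by paired or independent t-tests at p<0.05, and seven of the eight before-session readings are not untreated values. Following the plan as written, a transient post-session rise, even within one arm, could be reported as success on a primary outcome with no difference one day after treatment.

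The counts (25 and 7 of 8) follow from the documents. The 6 to 7 hour interval depends only on how the 8-hour gap is read. The SpO2 gains in steps 4 and 5 are illustrations, since the documents give no carry-over, effect size or SD for SpO2 or NES. The change should be made, but the point does not affect the PaO2/FiO2 outcome or the sample size.

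**What to change.** - Make the value one day after the last session the sole primary time point for SpO2 and NES, matching the other two primary items. Compare it between arms with adjustment for the Day 1 value taken before session 1, stating whether that is the item 1 baseline evaluation or the item 2 reading.
- Make the per-session and 6-hour readings secondary, labelled acute response, and compare them between arms against that same Day 1 value. Same-session change may be described but should not support an efficacy claim.
- Reconcile the visit schedule with the outcome list: define NES, schedule it at baseline and one day after at least, and either schedule the 6-hour reading or remove it. State whether the 8-hour interval runs from the start or the end of the first session.

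For SpO2 the primary change is wording only, as both readings needed are already scheduled. NES and any separate 6-hour reading need schedule entries. The price is that per-session readings no longer support a primary claim.
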